#### Table 4 Electrocardiogram, Pharmacokinetic, and Biomarker Assessments: M3541 Once per FD Dosing Schedule

ECG = electrocardiogram; FD = Fraction Day (days when RT and M3541 are given); PK = pharmacokinetics; PTD = post-treatment day.

a. 12-lead resting ECGs will be obtained after the subject has been in semi-supine position for at least 5 minutes and evaluated by the Investigator for safety assessment. All ECGs should be collected prior to any blood draws for routine clinical laboratory samples or any associated PK blood sample draws. The ECG should be obtained using a Holter recorder. An ECG on PTD 1 is only required if the PTD 1 optional PK sample is drawn.

b. At the indicated times, additional digital ECG recordings equivalent to triplicate ECGs are to be recorded for quantitative analysis by a central ECG laboratory (after the end of the study). The ECG recordings must be acquired immediately prior to the PK sample scheduled for the same time point. The ECG should be obtained using a Holter recorder.

- c. The 8 and 12 hour PK samples and ECG assessments are optional.
- d. The 72 and 240-hour timepoints correspond to PTD 1 and 8, respectively. The 72-hour PK sample is optional and will only be taken if the patient has a visit on PTD 1.
- e. The predose sample should be taken within 1 hour before dosing at each sampling day. PK and pharmacodynamic sampling should occur after any required ECG recording.

Table 5Electrocardiogram, Pharmacokinetic, and Biomarker Assessments: Thrice Weekly Intermittent M3541Dosing Schedule: Monday / Wednesday / Friday

	Predose	Hours Postdose (± minutes)										
		1 (± 5)	3 (± 30)	4 (± 30)	6 (± 30)	8 (± 30)	12 (± 30)	24 (± 120)	26 (± 120)	72 (± 24h)	240 (± 24h)	
Electrocardiogram a												
FD 1 (M3541 dosing)	Xp	Xp	Xp	Xp	Xp	X b,c	X b,c	X b,d	X b,d			
FD 3, 5, 6, and 8 (M3541 dosing)	Х		Х									
FD 10 (M3541 dosing)	Xp	Xp	Xp	Xp	Xp	X b,c	X b,c			X b,e	X b,e	
Pharmacokinetic f												
FD 1 (M3541 dosing)	Х	Х	Х	Х	Х	Xc	Xc	Xd	Xď			
FD 3, 5, 6, and 8 (M3541 dosing)	Х		Х									
FD 10 (M3541 dosing)	Х	Х	Х	Х	Х	Xc	Xc			Xe	Xe	
Plasma protein determination												
FD 1	Х											
FD 10	Х											
Pharmacodynamic marker CC												
FDs 1, 6, and 8	Х	Х	Х					FD 1 only				
FD 2	Х											
Immune cell sampling f												
FDs 1, 6, and 9	Х											

ECG = electrocardiogram; FD = Fraction Day (RT days); PK = pharmacokinetics; PTD = post-treatment day.

a. 12-lead resting ECGs will be obtained after the subject has been in semi-supine position for at least 5 minutes and evaluated by the Investigator for safety assessment. All ECGs should be collected prior to any blood draws for routine clinical laboratory samples or any associated PK blood sample draws. The ECG should be obtained using a Holter recorder. An ECG on PTD 1 is only required if the PTD 1 optional PK sample is drawn.

b. At the indicated times, additional digital ECG recordings equivalent to triplicate ECGs are to be recorded for quantitative analysis by a central ECG laboratory (after the end of the study). The ECG recordings must be acquired immediately prior to the PK sample scheduled for the same time point. The ECG should be obtained using a Holter recorder.

c. The 8 and 12-hour PK samples and ECG assessments are optional.

d. The 24 and 26-hour timepoints will happen on FD 2 and may be adapted, keeping a minimal interval of 2 hours between the 24 and the 26-hour samples

- e. The 72 and 240-hour post dose timepoints correspond to PTDs 1 and 8, respectively No M3541 dosing on this day. The 72-hour PK sample is optional and will only be taken if the patient has a visit on PTD 1.
- f. The predose sample should be taken within 1 hour before dosing at each sampling day. PK and pharmacodynamic sampling should occur after any required ECG recording.

Table 6Electrocardiogram, Pharmacokinetic, and Biomarker Assessments: Twice Weekly Intermittent M3541Dosing Schedule: Monday / Thursday

						Hou	rs Postd	ose (± mir	nutes)			
		1	3	4	6	8	12	24	26	48	96	264
	Predose	(± 5)	(± 30)	(± 30)	(± 30)	(± 30)	(± 30)	(± 120)	(± 120)	(± 120)	(± 24h)	(± 24h)
Electrocardiogram a,b												
FD 1 (M3541 dosing)	Xc	Xc	Xc	Xc	Xc	Xc,d	Xc,d	Xc	Xc	Xc		
FD 4 (M3541 dosing)	Х		X									
FD 6 (M3541 dosing)	Х		X									
FD 9 (M3541 dosing)	Xc	Xc	Xc	Xc	Xc	Xc,d	Xc,d	Xc	Xc		X c,e	X c,e
Pharmacokinetic f												
FD 1 (M3541 dosing)	Х	Х	X	X	X	Xq	Xq	X	Х	Х		
FD 4 (M3541 dosing)	Х		X					X	Х			
FD 6 (M3541 dosing)	Х		X					Х	Х	Х		
FD 9 (M3541 dosing)	Х	Х	X	X	X	Xd	Xd	Х	Х		X e,g	Xe
Plasma protein determination												
FD 1	Х											
FD 9	Х											
Pharmacodynamic marker CC												
FDs 1, 6, and 9	Х	Х	X									
FD 2	Х											
Immune cell sampling f												
FDs 1, 6, and 9	X											

ECG = electrocardiogram; FD = Fraction Day (RT days); PK = pharmacokinetics; PTD = post-treatment day.

a. 12-lead resting ECGs will be obtained after the subject has been in semi-supine position for at least 5 minutes and evaluated by the Investigator for safety assessment. All ECGs should be collected prior to any blood draws for routine clinical laboratory samples or any associated PK blood sample draws. The ECG should be obtained using a Holter recorder. An ECG on PTD 1 is only required if the PTD 1 optional PK sample is drawn.

b. In case dosing is delayed on FD 4 and FD 6, PK sampling will be done at dosing day. In case dosing is delayed from FD 9 to FD 10, the 24h and 26h ECGs and PK samples may be skipped.

CCI

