AE = adverse event; β-HCG = beta-human chorionic gonadotropin; BPI-SF = Brief Pain Inventory – Short Form; CT = computed tomography; ctDNA = circulating tumor DNA; DLT = dose-limiting toxicity; ECG = electrocardiogram; ECOG PS = Eastern Cooperative Oncology Group performance status; eCRF = electronic case report form; EoS = End-of-Study; FD = Fraction Day (days when RT and M3541 are given); FU = follow-up; Gy = Gray; HBV = hepatitis B virus; HCV = hepatitis C virus; HIV = human immunodeficiency virus; MRI = magnetic resonance imaging; PK = pharmacokinetics; PTD = Post-treatment Day (starting the day after the last dose of RT and M3541 until 1 year later); QTCF = Fridericia corrected QT interval; RECIST 1.1 = Response Evaluation Criteria in Solid Tumors version 1.1; RT = radiotherapy; TEAE = treatment-emergent adverse event.

Note: Where scheduled post-treatment visits coincide with a weekend or holiday, they may be postponed to the next working day (up to + 2 days). The relevance of any safety finding during this additional time in the context of a DLT or any other late toxicity will be reviewed by the Safety Monitoring Committee.

- a. All subjects will be followed up for disease progression until 1 year after RT is completed, or earlier due to any reason whereby tumor assessments are no longer applicable (eg, PD, if a new treatment is started, withdrawal of consent). The reason for early discontinuation should be captured in the source document. If EoS occurs prior to PTD 365, all assessments must be done as planned for PTD 365. All subjects will be followed for survival and for delayed AEs for up to 1 year (and beyond for AEs) from PTD1. After the 1 year follow-up, the Investigator will be asked to contact subjects every 3 months (± 1 month, phone call is acceptable) until the defined end of the study (see Section 5.7) to enquire and monitor for late appearing RT-related toxicity.

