- b. FD 1 is the first dose of M3541 and first fraction of RT. Planning of the RT will follow institutional guidelines and will start on a Monday (with the first Saturday and Sunday as a M3541 / RT holiday). In cohorts where required, subjects will be asked to stay overnight in a supervised environment on FD 1 unless the PK sampling and ECG assessment at 8 and 12 hours postdose can be completed otherwise. FD 10 is the last administration of M3541 / RT and the DLT follow-up period will start on the following day (PTD 1). In case of premature withdrawal from the study during the treatment period, the assessments scheduled for the visit on FD 10 should be performed. In such cases, this visit will be considered the EoS visit. If FD 10 is on a Friday then safety laboratory assessments and urinalysis (as required) must be done on FD 9.

- c. The 2-week DLT follow-up period (PTDs 1 through 14) starts on the day after the last administration of M3541 / RT. With the treatment period starting on a Monday, PTD 15 will land on a Saturday. The PTD 15 visit has a + 2 days visit window, thus subjects should present to the clinic on the following Monday for the PTD 15 DLT follow-up visit. PTD 22 will also land on a Saturday. The PTD 22 visit has a ± 2 days visit window, thus subjects should present to the clinic for this safety assessment on either the preceding Thursday/Friday (PTDs 20/21) or the following Monday (PTD 24). Subjects with ongoing AEs should present to the clinic throughout the DLT follow-up period as appropriate and instructed by the Investigator. See Section 6.5 and subsections for allowed and prohibited medications during the DLT period.
- d. Subjects must meet all inclusion criteria and not any exclusion criteria prior to enrollment. Hepatitis B and C results obtained within 3 months prior to screening are still valid for the purpose of this study. In the case of new clinical laboratory abnormalities detected prior to the first dose, the eligibility of the subject should be reconsidered.

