Pharmacodynamic markers in blood t			S	See Table	5						
Immune cell analysis u			S	See Table	5						

	Screening			Evaluati Thrice W		l (5 weeks hedule	;)	Short- term	Mid-term Safety FU	Long-term Safety FU	Survival FU / EoS a /
		Treatm		d (2 cons weeks) 1 + Palliat		alendar	DLT FU Period (3 weeks)	Safety FU			Post 1-Year FU
Study Periods	Day -21 to Day -1		FD 1 b to FD 10 b					PTD 22 to 30	PTD 31 to 90	PTD 91 to 180	PTD 181 to 365
FD / PTD (± visit window)	-21 to -1	FD 1, 6	FD 2, 7	FD 3, 8	FD 4, 9	FD 5, 10 b	PTD 22 c (± 2 Days)	PTD 30 (± 2 Days)	PTD 42, 90 (± 7 Days)	PTD 126, 180 (± 14 Days)	PTD 270, 365 (± 21 Days)
M3541 v		Х		Х		х			No Treatmer	nt	
RT 3 Gy/FD		х	x x x x x								
Follow-up for RT-related toxicity / survival w								x	x	x	Xw

AE = adverse event;  $\beta$ -HCG = beta-human chorionic gonadotropin; BPI-SF = Brief Pain Inventory – Short Form; CT = computed tomography; ctDNA = circulating tumor DNA; DLT = dose-limiting toxicity; ECG = electrocardiogram; ECOG PS = Eastern Cooperative Oncology Group performance status; eCRF = electronic case report form; EoS = End-of-Study; FD = Fraction Day (days when RT and M3541 are given); FU = follow-up; Gy = Gray; HBV = hepatitis B virus; HCV = hepatitis C virus; HIV = human immunodeficiency virus; MRI = magnetic resonance imaging; PK = pharmacokinetics; PTD = Post-treatment Day (starting the third day after the last dose of RT and M3541 until 1 year later); QTCF = Fridericia corrected QT interval; RECIST 1.1 = Response Evaluation Criteria in Solid Tumors version 1.1; RT = radiotherapy; TEAE = treatment-emergent adverse event.

- a. All subjects will be followed up for disease progression until 1 year after RT is completed, or earlier due to any reason whereby tumor assessments are no longer applicable (eg, PD, if a new treatment is started, withdrawal of consent). The reason for early discontinuation should be captured in the source document. If EoS occurs prior to PTD 365, all assessments must be done as planned for PTD 365. All subjects will be followed for survival and for delayed AEs for up to 1 year (and beyond for AEs) from PTD1. After the 1 year follow-up, the Investigator will be asked to contact subjects every 3 months (± 1 month, phone call is acceptable) until the defined end of the study (see Section 5.7) to enquire and monitor for late appearing RT-related toxicity.

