# 7.1.3 Dose-limiting Toxicity Evaluation Period

The DLT evaluation period will be 4 weeks in duration, including the 2-week treatment period (including a 2-day M3541 / RT holiday after FD 5) plus a 2-week DLT follow-up period that starts on the day after the last administration of M3541 / RT (see Figure 1). After the M3541 / RT treatment period, subjects will return to the clinic on PTD 15 (+ 2 days) for assessments (including the BPI-SF as applicable) as outlined in Table 1. The DLT evaluation period could exceed the 4-week period only if M3541 / RT has been interrupted and given over a period exceeding 2 weeks.

Subjects with ongoing AEs should present to the clinic throughout the DLT follow-up period as appropriate and instructed by the Investigator (see Section 6.5 and subsections for allowed and

prohibited medications). It is expected that the Investigator will follow his / her subjects and will ask subjects to come in to the clinic (and document) when AEs are known to happen. In absence of any new or major toxicity / AE during the DLT follow-up period, the subject need only be seen on PTD 15 (+ 2 days) and PTD 22 ( $\pm$  2 days).

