## Major Scientific Changes:

- The DLT follow-up period will now start on the day after the last dose of study treatment rather than 3 days after the last dose of study treatment
- The duration of the DLT follow-up period has been reduced from 3 weeks to 2 weeks. This modification ensures that study subjects who require additional anticancer treatment can receive it as soon as possible following dosing in the study. The 2-week DLT follow-up period reflects 5 times the half-life of M3541 (approximately 2 days) allowing for intersubject variability and is supported by the observation that there is no evidence that M3541 has an active metabolite with a half-life longer than that of M3541. It is therefore considered appropriate to modify the DLT follow-up period based on the half-life of M3541. In addition, based on the available safety data from subjects dosed in the first 2 cohorts, it is not anticipated that modifying the DLT follow-up period in this way will impact the safety data collected in the study. Moreover, to ensure any potential RT-related late toxicities (as may be enhanced by M3541) that occur sometime after the end of the DLT follow-up period are documented, subjects will continue to be followed-up for up to 1 year after treatment, as defined in the previous version of the protocol
- The washout period for prior anticancer therapies is now based on the elimination half-life of the respective therapy, up to a maximum of 15 days, rather than on a fixed 15-day period (exclusion criterion 1)
- Changes to the overall frequency/number of blood samples for PK and pharmacodynamic assessments. Specifically, some PK samples have been removed to reduce the overall volume of blood collected from subjects enrolled in the study. In addition, PK collection at the end of the treatment period will now be on FD 10 so that the highest M3541 plasma concentration experienced by subjects at the end of treatment can be monitored. Pharmacodynamic sampling times are also amended to provide a more comprehensive monitoring of target inhibition throughout the treatment period. Pharmacodynamic and PK sampling times have been matched

whenever possible, except for FD 4/FD 5 and FD 9/FD 10, where pharmacodynamic samples need to be collected 1 day earlier due to the need to process them within 14 hours.

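### Table 4 ties the 72 h and 240 h samples after FD 10 to PTD 1 and PTD 8, but under the current PTD definition those days fall at about 24 h and 192 h, outside the table's own windows

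*Protocol*

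**What the plan says.** Protocol Table 4 (once per FD schedule) places the last two FD 10 PK and ECG points at 72 h and 240 h postdose, each with a window of ± 24 h. Footnote d converts these to visit days: "The 72 and 240-hour timepoints correspond to PTD 1 and 8, respectively". It adds: "The 72-hour PK sample is optional and will only be taken if the patient has a visit on PTD 1". Footnote a makes the PTD 1 ECG conditional on that same optional PK sample. Neither footnote makes the 240 h point optional.

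The abbreviations under Table 1 define the day count: "PTD = Post-treatment Day (starting the day after the last dose of RT and M3541 until 1 year later". Table 1 footnote b says that after FD 10 "the DLT follow-up period will start on the following day (PTD 1", and footnote c gives the calendar: "With the treatment period starting on a Monday, PTD 15 will land on a Saturday".

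The amendment summary explains the change made by Amendment 4.0: "The DLT follow-up period will now start on the day after the last dose of study treatment rather than 3 days". The older count survives in the current Tables 2 and 3, for the intermittent schedules, where PTD is defined as "starting the third day after the last dose of RT and M3541 until 1 year later".

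On visits, Section 7.1.3 says: "In absence of any new or major toxicity / AE during the DLT follow-up period, the subject need only be seen on PTD 15", and then adds PTD 22. Table 1 has no visit column between FD 10 and PTD 15.

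**The concern.** Table 4 gives a site two instructions for the same sample, one in hours and one in post-treatment days, and under the current day count they disagree. A site working from the day label would draw too early. A site working from Table 1 and Section 7.1.3 would find no visit at which to draw the 240 h sample.

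As Table 4 reads, these are the only FD 10 PK samples and ECGs after 6 h, and the 240 h ECG is the only post-treatment ECG that is not optional. They matter because Protocol 3.1.5 reports an extrapolated half-life of more than 48 h, against the 8 h predicted, and Protocol 8.3.2 lists half-life and AUC to the last quantifiable sample among the FD 9 or FD 10 endpoints. A late sample that is missed cannot be recovered.

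**Working it through.** **Inputs.** From Table 4: targets of 72 h and 240 h after the FD 10 dose, with windows of 72 ± 24 = 48 to 96 h and 240 ± 24 = 216 to 264 h. From Table 1: PTD 1 is the day after FD 10. From Tables 2 and 3: PTD 1 is the third day after the last dose.

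**Formula.** Hours after FD 10 = 24 × (days from FD 10 to PTD k). That is 24 × k under the Table 1 definition and 24 × (k + 2) under the third-day definition.

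**Reproducing the footnote.** Its mapping comes out exactly under the third-day definition:
- PTD 1: 24 × 3 = 72 h
- PTD 8: 24 × 10 = 240 h

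**Under the definition that governs Table 4:**

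| Day | Hours after FD 10 | Target | Window | Early by | Before window opens |
|---|---|---|---|---|---|
| PTD 1 | 24 | 72 | 48–96 | 48 h | 24 h |
| PTD 8 | 192 | 240 | 216–264 | 48 h | 24 h |

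**Clock times.** Assuming dosing between 07:00 and 15:00 and sampling between 07:00 and 20:00, PTD 1 spans 16 to 37 h and PTD 8 spans 184 to 205 h. Neither reaches its window.

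**Days that fit.** 72/24 gives PTD 3 (window PTD 2 to 4), and 240/24 gives PTD 10 (window PTD 9 to 11). With a Monday start, FD 10 is trial day 12, a Friday, so PTD 3 and PTD 10 are trial days 15 and 22, both Mondays. The early columns of Figure 1 show the same pairing. Its later columns do not keep that 12-day offset (PTD 42 stands under trial day 56), so the figure is supporting evidence and the Table 1 definition decides.

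**Weekend note.** A note under Table 1 lets scheduled post-treatment visits that fall on a weekend or holiday slip by up to 2 days.
- FD 10 on Friday: PTD 1 and PTD 8 are Saturdays. Two days later gives 24 × 3 = 72 h and 24 × 10 = 240 h, on target.
- FD 10 on Monday (a standard course that loses one FD; the synopsis allows delays of up to 3 FDs): PTD 1 and PTD 8 are Tuesdays. The weekend provision does not apply, and the points stay at 24 h and 192 h.

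**Nominal labels.** The SAP Section 9 rule for FD 6 to 10 is (X + 1) × 24 + Y. It gives 11 × 24 + 72 = 336 h and 11 × 24 + 240 = 504 h, matching SAP Table 4. Samples drawn on PTD 1 and PTD 8 without the weekend shift would really be at 264 + 24 = 288 h and 264 + 192 = 456 h from first dose.

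**Size of a mislabelled concentration.** Assuming a single exponential decline over the interval, the ratio of observed level to the level the label implies is 2^(48/t½):
- t½ = 48 h (the floor in Protocol 3.1.5): 2.0
- t½ = 72 h (assumed): 1.6
- t½ = 96 h (assumed): 1.4

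**The case against.** The best defence is that practice would usually come out right. Table 4's columns state the hours and windows directly. In the default calendar both days are Saturdays, and the weekend note moves them to Mondays that hit the targets. This stands for a Friday FD 10. It does not make the footnote correct: the note is permissive, it speaks of scheduled visits while Table 1 lists neither PTD 1 nor PTD 8, and it gives nothing when FD 10 is not a Friday.

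The second defence is that the analysis is largely protected, and most of that stands too. SAP 16.1.1 and 16.1.2 calculate PK parameters from actual times, so a correctly recorded early sample does not bias them. A reader might infer that the end-of-treatment half-life would fail the SAP's requirement of three terminal points. However, SAP 16.1.2 limits half-life and its regression diagnostics to FD 1, so that rule does not govern FD 10. The accumulation ratios use the first 6 h and Cmax only. SAP Table 4 covers ECG, pharmacodynamic and immune samples, not PK. The QTcF plots in SAP 15.7 stop at 250 h, so the 336 h and 504 h points are not drawn, and the worst-QTcF tables do not depend on the label.

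Third, a possible gap between 6 h and 240 h follows from the 72 h sample being optional. It would remain possible with a correct footnote.

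Finally, it overstates the case to say that a site following Section 7.1.3 would draw nothing. Sections 7.1 and 7.5 send sites to Table 4 as well. The text is in tension on the 240 h visit; it does not waive the sample.

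**Conclusion.** The contradiction is in the current text, not only in the amendment log. Under the Table 1 definition, footnote d places both late FD 10 points 48 h early and 24 h outside their windows. The effect remains wherever the weekend shift is not used or FD 10 is not a Friday. Separately, Table 1 and Section 7.1.3 name no visit for the 240 h sample that Table 4 requires.

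The consequences are confined to out-of-window or missed late FD 10 samples and ECGs, and to nominal-time concentration summaries and mean profiles. For the latter, the factor of about 2 assumes a 48 h half-life, single exponential decline, and a sample drawn on the labelled day yet reported under the nominal hour. The primary DLT endpoint is untouched.

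A reader might also infer that most subjects at 200 mg and all at higher doses were mis-sampled. The documents do not support that: they report one subject at 200 mg when the amendment was submitted, and give no site implementation dates, later enrolment or actual sampling days.

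Severity: should-fix.

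Tables 5 and 6 need no change on this point. Their day labels agree with the third-day definition in Tables 2 and 3, and SAP Section 7 says the intermittent schedules were never explored.

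**What to change.** 1. In Table 4 footnote d, replace PTD 1 and 8 with PTD 3 and 10, or drop the day labels and state the points in hours with their windows.
2. Align the PTD 1 wording in footnotes a and d, so that the optional 72 h PK sample and its ECG depend on the same, correctly numbered visit.
3. Reconcile Table 1 and Section 7.1.3 with the 240 h (PTD 10) PK sample and ECG that Table 4 already requires.
4. In the SAP, give the nominal 72 h or 240 h label only to samples inside the ± 24 h window. List those outside it at their actual time and leave them out of nominal-time means.

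The cost is a text correction in the next amendment or a clarification letter, plus one SAP programming rule. No sample is added. The one real burden is that step 3 formalises a clinic visit that Table 4 already implies but Table 1 does not show.
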